Exercise Interventions. After completing V2, we will randomize the subjects to one of three 16-week interventions: (i) RE, (ii) REALPA breaks in ST, or (iii) RE+AE (**Figure 3**). The RE+AE group serves as the standard of care. The RE group will complete supervised RE (2 x/wk). The REALPA breaks in ST group will complete a supervised RE (2 x/wk) and regular unsupervised LPA breaks in ST (5 d/wk, 6x10 min breaks/d at 2 METS (~30-40% VO_2 peak), ~500 kcal/wk above resting metabolism). The RE+AE group will complete supervised RE (2 x/wk) and calorically matched moderate intensity AE (3 d/wk, 50 min/session at 4 METS (~60-75% VO_2 peak), ~500 kcal/week above resting metabolism). The RE component for all 3 groups will consist of 3 sets of 10-12 repetitions to failure for a total of 8 exercises targeting the large muscle groups (**Table 2**). The AE component for the RE+AE group will consist of treadmill walking at ~4 METs for 50 min

(Table 2). The RE and AE sessions will take place in LSU School of Kinesiology's Exercise Training Facility under direct supervision (Drs. [name], [name], and [name] with the assistance of trained graduate students). All supervised exercise sessions will include a 5 minute warm-up and cool-down on either a bike or treadmill. We will provide subjects flexibility on the days per week that they can complete their exercise sessions. Note: The start of the exercise intervention will be at least 5 days post V2 to allow for adequate recovery from the muscle biopsy, but no more than 6 weeks after V2. Up to 2 weeks may be added to a subjects exercise intervention, to allow for potential make-up of missed exercise sessions and to provide flexibility for scheduling study visits.

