11. **Muscle Biopsies.** A *vastus lateralis* muscle biopsy will be performed using the technique of Bergstrom as described in SOP 906 from the PBRC Inpatient Unit by a trained Nurse Practitioner or physician. For *vastus lateralis* muscle biopsies, the risks are mild to severe pain, soreness, bruising and a small scar are common risks. There is a small risk of a hematoma (collection of blood in the tissue) or infection at the biopsy site. There is also a slight risk that a superficial nerve may be cut; the nerve may heal, or it may result in a permanent loss of sensation in the skin at the biopsy site. Sterile technique will be used to minimize infection risks and the biopsy site will be monitored closely. To reduce the risk of hematomas and bleeding, we ask that subjects stop taking anticoagulants, non-steroidal anti-inflammatory (NSAIDs), and aspirin for a week before and after the biopsy procedure. We will exclude individuals who cannot stop their anticoagulants. Previous data suggest that the rates of adverse events following a percutaneous muscle biopsy in older adults (60-76 years) are similar to those of younger adults.⁴¹ Moreover, [name] previously conducted a study at PBRC that included biopsies in elderly adults (70-84 years) with no serious adverse events.⁴² The PI has led and been involved in multiple studies that included muscle biopsies in both young (18-30) and older adults (65-85 years).^{15, 43-45}
12. **Archive of Biological Sample (blood and muscle biopsy tissue).** The primary risk to subjects who donate bio-samples to be banked for future research (molecular in this case) is the risk of loss of confidentiality and/or privacy. Most banks need to maintain a link between the identities of donors and coded specimens to be able to collect valuable clinical follow-up information about the donor. We will, however, create and maintain a firewall between the source and the researcher so that the protected health identifiers are never given to the researcher(s). Storage and disposal of tissue will be conducted in a manner conforming to the appropriate care and handling of biological specimens as outlined through the Institutional Biohazard Committee Guidelines.

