18. Exercise Interventions. The risks associated with the three exercise training interventions are those commonly associated with moderate to vigorous physical activity in older adults. The proposed exercise interventions are unlikely to cause major problems. We have conducted numerous exercise training studies and have never had a serious adverse event. There is the possibility of adverse events ranging from minor musculoskeletal problems to, in very rare cases, cardiovascular events. Occasionally study subjects experience minor orthopedic problems, but most are self-correcting with rest and standard first aid. These orthopedic injuries will be minimized by gradually progressing subjects to their prescribed dose at the start of the study and, if necessary, alternating exercise sessions between cycle ergometers and treadmills. Exercise supervisors are trained in first aid and basic CPR. All RE and AE sessions will be supervised by trained personnel in the LSU's School of Kinesiology's Exercise Training Facility. The LSU School of Kinesiology's Exercise Training Facility is well equipped with emergency response equipment including automatic defibrillator. Although some study subjects will be at moderately elevated risk for CVD, they will receive a thorough health screen including a physical examination by a study physician and a maximal exercise test. According to the available data on adverse events resulting from the types of exercise proposed here, risk should be low in this study. Fatal events during exercise are extremely rare.¹⁶ All resistance exercise (RE) and aerobic exercise (AE) training sessions will be supervised by a trained exercise specialist. The risk associated with the low intensity physical activity breaks in sedentary time are unlikely to cause any major problems. Prior to each exercise session, resting blood pressure, heart rate, and clinical symptoms will be assessed. Subjects will not be allowed to commence their exercise session if they have an absolute contraindication exercise,¹⁶ which includes

- a. Unstable Angina
- b. Resting systolic blood pressure > 200 mm Hg or diastolic blood pressure > 110 mm Hg
- c. Uncontrolled sinus tachycardia (resting HR >120 beats/min)

19. MMTT. There is a possibility of pain, bruising, or infection at the site of the needle insertion for the IV line. Trained personnel minimize this risk. The drink may make cause nausea, vomiting, abdominal bloating, or a headache.

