collected at LSU, and we will enter the data into a RedCap database under the direction of the study team's biostatistical consultant. We will routinely transfer the original data collection forms (e.g., questionnaires) from LSU to PBRC to ensure that each subject's records are up to date. The PI, Co-I's, medical consultant, and biostatistical consultant will review all data. The privacy of the study subjects is very important to PBRC, LSU, our study team, and we will protect the privacy of the study subjects as much as possible. In compliance with HIPAA requirements, we will not send out the names, addresses, phone numbers, social security numbers, or any other identifying information on our study subjects. If study data and / or study samples are sent outside of the LSU for further analysis, these data and / or samples will be de-identified. Similarly, any publications generated from the data collected from the proposed studies will exclude identifiers.

3. Data Safety Monitoring Plan (DSMP)

Overview of DSMP. Efforts to minimize the potential risks of the assessment methods and outcome variables include frequent monitoring by the investigators to assure that no volunteer suffers any adverse effects from participating in the research. The study team has extensive experience in all procedures and aspects of the study. The study team will review any subject safety issues as they occur and monthly research meetings. We will use an investigators committee to review the safety data in aggregate once a month. Our investigators committee will include the PI, Co-I's, and medical director ([name]). The PBRC's Institutional Review Board will also continuously monitor the proposed study for subject safety throughout the study period.

Safety Monitoring. In this study, an **adverse event or experience** is defined as any health-related unfavorable or unintended medical occurrence that happens throughout study participation. Examples of adverse events include but are not limited to the following:

- A clinically significant laboratory or clinical test result.
- An event that results in missing a study visit.
- An event that requires a visit to a physician.
- An event that occurs as a result of a study procedure.
- Unanticipated or untoward medical events that are not plausibly pregnancy related and may be study related.

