LSU and PBRC is committed to ensuring and maintaining the safety of its subjects. We will use the AAHRPP provided definitions of Adverse Events and Serious Adverse Events. We will report adverse events according to the institutional reporting policy provided by AAHRPP.

A **serious adverse event** (SAE) is defined as an unanticipated medical occurrence that is deemed associated with study participation by the study Medical Investigator that results in one of the following:

- Death
- Life-threatening event
 - Life threatening events in the mother or fetus are defined as those that in the view of the research staff and PI put the individual patient at imminent substantial risk of dying, or if continued participation in the study might have resulted in death.
- Hospitalization
- Disability or permanent damage
- Medical Intervention to prevent permanent impairment or damage

All AEs from date of consent will be reported. Adverse events will be documented during the scheduled visits. For each sign, symptom or adverse event, the following information will be recorded:

- A brief descriptor of the adverse event
- Start and stop dates
- Intensity (mild / moderate / severe)
- Whether the AE was "serious" or not (as defined below)

- Causal association with the intervention assigned (none / doubtful / possibly / probably / very likely)
- Outcome (resolved / resolved with sequelae / improving / still present and unchanged / death)
- Action taken with respect to the intervention (none / intervention temporarily discontinued / medical therapy required / intervention permanently discontinued / other).

Adverse event data will be collected from the date of consent until the final visit. Adverse event data will be analyzed quarterly, but serious or life-threatening adverse events may require immediate reporting and follow-up. We anticipate most adverse events will be mild and the subject will be able to resume activities within a day or two of reporting the event. Adverse Event reporting will follow the requirements of the IRB. Only adverse events that qualify as unanticipated problems will be reported to the IRB. Unanticipated problems involving risks to subjects or others include incidents only if the incident is unexpected, related or possibly related to participation in the research, and indicated that subjects or others are at a greater risk of harm than was previously known or recognized.

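### The only serious adverse event definition written out also requires the event to be unanticipated and study-related, so if it governs the flag, unrelated or anticipated deaths, hospitalisations and disabilities are marked not serious

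*Combined protocol and SAP*

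**What the plan says.** Under Safety Monitoring in the Data Safety Monitoring Plan, an AE is "any health-related unfavorable or unintended medical occurrence that happens throughout study participation". Neither cause nor expectedness enters that definition, and AEs are collected from consent to the final visit.

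The same section then says: "We will use the AAHRPP provided definitions of Adverse Events and Serious Adverse Events". The text of those definitions is not given. The one SAE definition that is written out "is defined as an unanticipated medical occurrence that is deemed associated with study participation by the study Medical Investigator", and the event must result in one of five outcomes: death, a life-threatening event, hospitalisation, disability or lasting damage, or an intervention to prevent lasting damage.

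Each AE record carries a flag for whether the event was serious "or not (as defined below"). No SAE definition follows that point. The record also has a separate causality item: "Causal association with the intervention assigned (none / doubtful / possibly / probably / very likely"). The outcome item includes death among its levels.

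Item 11 of Potential Risks, on muscle biopsies, warns that if a superficial nerve is cut, "it may result in a permanent loss of sensation in the skin at the biopsy site". The first biopsy is at V2, and the Exercise Interventions text says: "After completing V2, we will randomize the subjects to one of three 16-week interventions".

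**The concern.** Seriousness normally describes what happened to the participant. Whether the study caused the event, and whether it was foreseen, are separate questions. The written definition makes all three conditions for one label, and two of them are judgements. Relatedness rests with one named role. Expectedness rests with nobody in particular, because the word has no definition here. The nearest text explains unanticipated problems for IRB reporting and is not tied to the SAE definition.

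The study enrols adults aged 65 to 80, and adverse event reporting is its only safety endpoint. An SAE tabulation made under this wording would omit deaths and hospitalisations judged unrelated, as well as study-caused harm judged to have been anticipated. The omitted events could also miss the *serious* trigger for possible immediate reporting. A reader of the pilot results, including someone planning the follow-up trial, could not tell whether a low SAE count reflected few serious outcomes or the filter.

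**Working it through.** The plan gives no figure to reproduce and no arithmetic applies. The check sets the definitions side by side and follows example events through them.

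**The rules as written**

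- AE: any unfavourable or unintended medical occurrence during participation.
- SAE, written definition: unanticipated AND deemed associated with participation AND at least one of the five outcomes.
- SAE, outcome-only definition, for comparison: an AE with at least one of the five outcomes.

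**Example events**

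| Event | AE? | Written definition | Outcome-only |
|---|---|---|---|
| Hospitalisation, unanticipated, judged related | Yes | Serious | Serious |
| Hospitalisation, unanticipated, judged unrelated | Yes | Not serious | Serious |
| Death, judged unrelated | Yes | Not serious (outcome field shows death) | Serious |
| Permanent sensory loss from the study biopsy, judged related and anticipated | Yes | Not serious | Serious |

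The fourth row assumes that a risk named in advance counts as anticipated. The documents do not say so, but they do not rule it out, and this risk is named in Potential Risks. On that assumption, lasting damage caused by a study procedure fails the definition even though its relatedness is accepted.

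**Overlap with the causality item**

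The causality item allows a level of *none*. Under the written definition, an event judged unrelated to participation cannot be an SAE, so *none* is almost incompatible with *serious*. The exception is an event caused by a study procedure and not by the exercise programme: the definition refers to study participation, whereas the causality item refers to the assigned intervention. That difference in scope matters at V2. The biopsy there precedes randomisation, so no intervention has been assigned and the item as worded does not fit.

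**Which definition governs the flag**

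1. AAHRPP definitions: adopted by name, text not supplied.
2. The written definition: supplied, but it stands above the flag, not below it.
3. A definition below the flag: none exists.

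The written definition is the only text in the documents that can be applied, but the documents do not establish that it governs.

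**The case against.** The strongest reply is that the effect on the flag is conditional. The plan names the AAHRPP definitions before it writes its own, and if those govern and differ, the flag may work as it should. This stands, and it is why the conclusion is stated as conditional. It does not remove the need for a correction. If the two definitions agree, the restriction is real; if they differ, the protocol has two definitions and a pointer to neither.

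A second reply is that little is lost in practice. Much of this also stands. All AEs are recorded, with descriptor, dates, intensity, causality, outcome and action taken. A death is visible in the outcome field. The Overview of DSMP provides for team review as issues arise, monthly aggregate review by an investigators committee, and continuing IRB monitoring. No SAE count or proportion is a planned endpoint. The immediate-reporting step is only permissive, and it names life-threatening events alongside serious ones. What remains is that hospitalisation and disability have no outcome level of their own. Without the flag they must be picked out of the free-text descriptor or inferred from other fields.

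Three stronger readings are tempting, and the documents do not support them:

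- A reader might infer that unrelated deaths go unrecorded. They do not, because the AE definition captures them.
- A reader might infer that the wording keeps events from the IRB. IRB event reporting follows its own rule on unanticipated problems, does not use the serious flag, and would be unchanged by the correction.
- A reader might take "Fatal events during exercise are extremely rare" in the Exercise Interventions risk item as proof that an exercise death would be classed as anticipated. That sentence is weak evidence, since it sits among statements that major problems are unlikely. The biopsy example is firmer, but it too rests on the assumption stated above.

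**Conclusion.** The concern holds in conditional form. The only SAE definition written out adds two conditions, one undefined and one a causality judgement, to all five outcomes. If it governs the flag, events with a listed outcome that are judged unrelated or anticipated are marked not serious. Whether it governs cannot be settled from the documents, and that ambiguity is itself a defect.

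The size is qualitative. The documents state no SAE rate, so the number of events affected cannot be given. The loss is confined to the seriousness classification and anything built on it. AE capture, the visibility of deaths and IRB event reporting are unaffected. This should be corrected; given the monitoring in place, the documents do not show participants left without safety oversight.

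**What to change.** State one governing SAE definition based on outcome alone: any AE that results in one of the five listed outcomes. Remove the *unanticipated* condition and the condition that the Medical Investigator deem the event associated with participation. Reconcile the wording with the cited AAHRPP definitions, and point the flag to the agreed text.

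Keep relatedness as its own item, worded to cover study procedures as well as the assigned intervention, so that it fits events arising from the V2 biopsy. Add expectedness as a separate item. The IRB rule on unanticipated problems can stay as it is.

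The cost is a short protocol correction and one or two form fields. The reported SAE count may be higher than under the present wording.

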Table 2. The RE group will complete supervised RE (2x/wk) (A). The REALPA breaks in ST group will complete supervised RE (2x/wk) and regular unsupervised LPA breaks in ST (5x/wk) (A+B). The RE+AE group will complete supervised RE (2x/wk) and calorically matched moderate intensity AE (3x/wk) (A+C).

Physical Activity Monitoring During Intervention. To quantify total physical activity throughout the intervention, we will ask that subjects wear a physical activity monitor (Actigraph, GT9X) on their wrist 24 h/d for the duration of the study and a second physical activity monitor (Actigraph, GT9X) on their thigh during weeks 1, 4, 8, 12, and 16 for further quantification. We will screen raw data from these monitors for periods of valid wear-time with a required minimum wear-time of 10 h per valid wear-day and 4 valid wear-days per week.^{23,24} We will use standard algorithms to characterize the patterns of PA and ST.²⁵

Adherence Monitoring During Intervention. We will monitor each subject's attendance to the prescribed exercise training sessions and exercise training logs to assess adherence to the exercise intervention. We will also use the physical activity monitoring data to help assess adherence to the exercise intervention. De-identified physical activity monitoring data will be uploaded to the CentrePoint Cloud-Based Data Capture and Management Platform to facilitate data collection and monitoring.

Visit 3 (V3) (End of Exercise Intervention). During last week of the intervention (i.e., week 16), subjects will be asked to complete V3, with two parts. Part I will occur PBRC and Part II at the LSU Exercise Physiology Laboratory on the main campus of LSU.

V3, Part I (about 2 hours).

After an overnight fast (> 10 hours), subjects will report to PBRC to complete V3, Part I. During this visit, we will measure height, weight and vital signs. We will then perform the SPPB and Exercise Test (VO₂ Peak).

V3, Part II (about 1 hour).

Subjects will report to LSU Exercise Physiology Laboratory to complete V3, Part II (non-fasted). The visit procedures for this visit can be done at a regularly scheduled exercise session and would be completed prior to the start of that day's exercise. During this visit, we will conduct the Biodex, 1-RM, and Handgrip Strength and Endurance Testing.

Posttraining Visit 4 (V4) (About 5 hours).

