After an overnight fast (> 10 hours), study subjects will report to LSU Exercise Physiology Laboratory to complete V4. V4 will be scheduled 48 hours after the subject's last training session. During this visit, we will measure height, weight and vital signs. During this visit, we will ask subjects to complete the International Physical Activity Questionnaire-Elderly,¹⁹ Sedentary Behavior Questionnaire,²⁰ and PROMIS Physical Function Questionnaire^{21, 22}, and the Pittsburgh Fatigability Questionnaire. We will also measure the body composition by DXA and BIA. We will also perform the MMTT as described for V1. We will also draw fasting and MMTT associated bloods as described for V2 (total blood volume of about 150 ml or 10-12 tablespoons total). The analyses performed on these blood samples collected in V4 will be as described for V2.

Posttraining V5 (About 3.5-4 hours)

After an overnight fast (> 10 hours), study subjects will report to PBRC to complete V5. V5 will be scheduled about 72 hours after the subject's last training session. During this visit, we will measure height, weight and vital signs. We will measure body composition using standard circumferences, optical imaging, and BIA, which will be conducted in [name] Laboratory. During this visit, we will collect a fasting blood sample (~ 10 ml). We will also perform the MRI for leg muscle mass, Phosphorous Magnetic Resonance Spectroscopy – ³¹P-MRS, and Muscle Biopsy as described for V3. During V5, subjects who agree to the optional Carbon-13 magnetic resonance spectroscopy procedure will do that procedure.

STUDY ENDPOINTS

Primary Endpoints

1. Comparison of within and between group changes in muscle strength, mass, and quality (strength/mass) using isokinetic dynamometry and DXA (primary outcomes Aim 1) between treatment groups.
2. Comparison of within and between group changes in body composition by DXA, fasting blood glucose and lipids by a clinical chemistry panel and glucose tolerance by a mixed meal tolerance test (primary outcomes Aim 2)

Safety Endpoints

1. Safety will be monitored by adverse event reporting (See Data Safety Monitoring Plan).

DETAILED METHODS AND ANALYSIS

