Exercise Interventions. The RE group will complete 16 weeks of supervised RE training (2 x/wk). The REALPA breaks in ST group will complete 16 weeks of supervised RE training (2 x/wk) and regular unsupervised LPA breaks in sedentary time (5 d/wk, 6x10 min breaks per day at 2 METS (~30-40% VO₂ peak), ~500 kcal/wk above resting metabolism). The RE+AE group will complete 16 weeks of RE (2 x/wk) and calorically matched moderate intensity AE (3 d/wk, 50 min/session at 4 METS (~60-75% VO₂ peak), ~500 kcal/week above resting metabolism). The RE component for all three groups will consist of 3 sets of 10-12 repetitions to failure for a total of 8 exercises targeting the large muscle groups (See Research Strategy for Details). The RE and AE sessions will take place in LSU School of Kinesiology's Exercise Training Facility under direct supervision (Drs. [name], [name], and [name] with the assistance of trained undergraduate and graduate students). Over the first month of the intervention, we will be progressively increase the intensity and volume of the exercise prescriptions to the targeted training intensities and volumes to reduce the risk of injury and muscle soreness. Prior to each RE and/or AE training session, we will assess resting blood pressures, heart rates, and clinical symptoms. We will not allow subjects to exercise if they have an absolute contraindication to exercise (see Potential Risks Section

Below). We will also assess heart rates using heart rate monitors (e.g., Polar or Zephyr Bioharness) and ratings of perceived exertion (RPE, Borg 6-20) throughout the supervised exercise sessions.

b. Sources of Materials.

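### Adverse-event collection is tied to undefined scheduled visits, and symptom checks are nominally 2.5 times as frequent in RE+AE as in RE or REALPA, so by-arm event counts may not be comparable

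*Combined protocol and SAP*

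**What the plan says.** Under Study Endpoints, the only safety endpoint is "Safety will be monitored by adverse event reporting", with a pointer to the Data Safety Monitoring Plan. The Safety Monitoring part of that plan says "Adverse events will be documented during the scheduled visits" and requires a descriptor, start and stop dates, intensity, causality and outcome for each sign, symptom or adverse event. Collection runs from consent to the final visit, with monthly aggregate review and quarterly analysis.

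The term scheduled visits is not defined. Table 1 lists V1 to V5 and has no adverse-event row. The main Exercise Interventions text, where it places the weekly weighing, also calls training sessions scheduled visits.

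The Exercise Interventions paragraph under Risks to Human Subjects says "Prior to each RE and/or AE training session, we will assess resting blood pressures, heart rates, and clinical symptoms". Item 18 of Potential Risks repeats the symptom check and adds "All RE and AE sessions will be supervised by trained personnel in the LSU's School of Kinesiology's Exercise Training Facility". By Table 2 and its note, RE and REALPA each have two supervised sessions a week. RE+AE has two RE and three AE sessions. The LPA breaks in REALPA are unsupervised.

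**The concern.** A mild event that comes and goes between contacts is recorded only if someone asks about it or the subject mentions it. When staff see one arm five times a week and the others twice, and look for symptoms each time, the arm seen more often can show more events at the same true risk. Here that arm is RE+AE, which the protocol calls the standard of care.

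This bears on the trial's own argument. The background names fear of adverse events as a barrier to exercise in older adults, and the benefits sections suggest that REALPA may be more practical than RE plus moderate AE. A by-arm adverse-event table carried into the follow-up R01 application would bear on that comparison, and part of any difference in it could come from how often subjects were asked.

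**Working it through.** The plan gives no figure for contacts or event rates by arm, so there is none to reproduce.

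**Contacts.** Inputs: 2 RE sessions a week in all arms, 3 AE sessions a week in RE+AE, 16 weeks.

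- RE and REALPA: 2 × 16 = 32 each.
- RE+AE: (2 + 3) × 16 = 80.
- Ratio: 80/32 = 2.5.

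These counts are nominal. Adding 3 or 4 post-randomisation study visits to each arm (V3 in one or two parts, V4, V5) gives 83/35 = 2.37 or 84/36 = 2.33. The protocol allows flexible training days. If every RE session shares a day with an AE session, contact days are 3 against 2 a week, a ratio of 1.5. The Randomization paragraph says 12 weeks where other sections say 16. That needs reconciling, but 60/24 is also 2.5.

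**Two readings of scheduled visits.**

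- *Training sessions included:* the contact ratio is about 2.5 for RE+AE against either other arm, and 1.0 for REALPA against RE.
- *V1 to V5 only:* the ratio is 1.0 throughout. V1 and V2 precede randomisation and V3 falls in week 16, so about 15 weeks of training pass without a study visit.

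**Possible effect on recorded events.** Assume, as a worst case, that an event is noted only if present on a contact day. Take Table 2's days (Tuesday and Thursday for RE and REALPA, Monday to Friday for RE+AE) and let an event start on any day of the week with equal probability. Detection is the share of the seven start days for which the event overlaps a contact day.

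| Event length | RE, REALPA | RE+AE | Ratio |
|---|---|---|---|
| 1 day | 2/7 (29%) | 5/7 (71%) | 2.5 |
| 2 days | 4/7 (57%) | 6/7 (86%) | 1.5 |
| 3 days | 5/7 (71%) | 7/7 (100%) | 1.4 |
| 4 days | 6/7 (86%) | 7/7 (100%) | 1.17 |
| 5 days or more | 7/7 | 7/7 | 1.0 |

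With full recall since the last contact, the ratio is 1.0 at every length. The longest gap to be recalled is 5 days in RE and REALPA (Thursday to Tuesday) and 3 days in RE+AE (Friday to Monday).

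**The case against.** The strongest reply is that the plan contains no safety comparison to bias. The primary endpoints speak of within- and between-group changes, but the safety endpoint does not. The statistical section compares arms on outcomes and adherence only, and the investigators committee reviews safety data in aggregate. This stands: what is at risk is a descriptive or later table, not a planned test.

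Second, the recording rules reach beyond events present on the day. Start and stop dates, a resolved outcome and collection from consent to final visit bring events between contacts into scope, and safety issues are reviewed as they occur. With recall over gaps of at most 5 days, the distortion could be close to nil. This also stands, and it is why only a range can be given.

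Third, the pre-session check serves to decide whether a subject may exercise, and the main Exercise Interventions text lists only blood pressure and heart rate. This stands in part. The risk sections add clinical symptoms, and the safety plan requires a record for each sign or symptom, so a finding at that check would enter the data.

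A reader might infer more than the documents support:

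- *That the plan expects most events to last a day or two.* It says that subjects should resume activities within that time after reporting, which is not event duration.
- *That the unsupervised LPA bouts (nominally 6 × 5 × 16 = 480) go unchecked.* REALPA subjects are seen twice weekly and have logs and monitors, although these are described for adherence. The first-month ramp-up makes 480 a ceiling. What is missing is an adverse-event question covering those days.

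**Conclusion.** The point holds as a minor design weakness. Symptom checks are unequal by design between RE+AE and the other two arms, nominally 80 against 32, and no question at a common interval is stated. If training sessions count as scheduled visits, ascertainment of short, mild events is unequal. If they do not, it is equal but rests on long recall or spontaneous report. Monthly review and quarterly analysis fit the first reading better, but do not settle it.

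It would be wrong to conclude that REALPA will look safer than RE+AE by a factor of 1.5 to 2.5. The 2.5 is a ratio of contacts. The ratio of recorded events, at equal true risk, lies between 1.0 and 2.5 depending on event duration and recall, neither of which the documents give. Nor does the problem reach supervised contacts in REALPA against RE, the contrast in the central hypothesis, where sessions are 2 against 2 a week. RE+AE also involves more supervised exercise than RE alone and higher-intensity activity than REALPA, so a higher count there could be real. As written, the plan could not separate that from more frequent checking.

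**What to change.** Ask one structured adverse-event question, with one-week recall, once a week in every arm at an RE session. The session at which weekly weight is taken would serve, since every arm already attends it. Add the question as a row in Table 1 and define scheduled visits in the Safety Monitoring section. Base any by-arm adverse-event table on these answers, label the table descriptive, and report the number of weekly questions answered in each arm.

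Events found at other contacts, including pre-session checks and spontaneous reports, are still recorded and reported, flagged by source. No safety reporting is lost.

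This brings the ratio of planned questions to 1.0 and extends the recall window over the unsupervised LPA days. It does not remove a real difference due to exercise exposure, and should not. The cost is a few minutes a week at existing sessions, one form, and slightly more minor events recorded.
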